7.2. ADVERSE EVENTS

Adverse events (AEs) will be coded using MedDRA V24.1. All treatment-emergent AEs (TEAEs) from the start of trial drug dosing will be collected.

Treatment-emergent AEs are defined as AEs with onset date on or after the first day of exposure to investigational product. Unless otherwise stated, all outputs will be presented for treatment-emergent AEs and, for simplicity, referred to as AEs.

Related AEs are defined as events classified as 'possibly related' or 'probably related' by the investigator.

Severity categories will include mild, moderate, and severe. Any missing severity will be imputed as severe prior to selecting the report that will contribute to the summary. As a result, a patient would be counted as severe due to a missing severity, even if the patient reported similar events at a lesser degree of severity. The same logic will be applied to the related AEs.

For patients who permanently discontinued treatment due to an AE and who also withdrawal trial prematurely, the AE leading to treatment discontinuation is counted as an AE leading to trial withdrawal (regardless of the cause marked as leading to trial withdrawal).

Common AEs are defined as events (preferred terms) occurring in \geq 5% of patients in the glepaglutide 10 mg OW or glepaglutide 10 mg TW treatment groups.

For all AE tables summarized by SOC and PT, a patient contributes only once to the count for a given AE on the SOC level and on the PT level within SOC. AE incidence tables will be sorted by descending frequency counts in hierarchical order of glepaglutide 10 mg twice weekly, then by glepaglutide 10 mg once weekly, and then by placebo. PTs will be sorted in similar hierarchical fashion within the SOC.

If there are less than 5 AEs of a type (AEs leading to treatment discontinuation, AEs leading to trial withdrawal, AESIs or AEs in other safety areas of interest) in the entire observation period, then only a listing will be prepared.

The following AE summaries will be presented by treatment group and will present the following information:

- n: number of patients experiencing at least one AE
- %: percentage of patients experiencing at least one AE
- E: number of AEs
- R: event rate (calculated as the number of AEs divided by PYO multiplied by 100)

An overall summary table will include the number and percentage of

- All adverse events
- Serious adverse events

25 August 2022

- Severity (Mild, Moderate, Severe, Missing)

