- Relationship (Possibly, Probably, Unlikely, Not Related, Missing)
- AEs leading to trial withdrawal
- AEs leading to treatment discontinuation
- AEs leading to treatment pause
- Outcome (Recovered/Resolved, Recovering/Resolving, Recovered/Resolved with Sequelae, Not Recovered/Not Resolved, Fatal, Unknown, Missing)

Additional AE tables will include:

- AEs by System Organ Class (SOC) and Preferred Term (PT)
- AEs Occurring in >=5% of Patients Treated with Glepaglutide by SOC and PT
- Summary of Serious AEs
- Serious AEs by SOC and PT
- Related AEs by SOC and PT
- Severe AEs by SOC and PT
- Moderate AEs by SOC and PT
- Mild AEs by SOC and PT
- AEs of Special Interest (AESIs) by Type and PT
- Other safety areas of interest (see Table 8) by SOC and PT

Other safety areas of interest are defined based on:

- their relevance for the SBS population or known class effects with other glucagon-like peptide-2 (GLP-2) receptor agonists (RAs) (e.g. gastrointestinal stenosis and intestinal obstruction [including stoma complications]; fluid retention and volume overload; hepatic disorders)
- general applicability to injectable peptide drugs (e.g. injection site reactions; hypersensitivity reactions)
- general interest for any new drug administered long-term (e.g. rare events; adverse event by organ system or syndrome [e.g., cardiac, renal and hepatic events]).

For these other safety areas of interest, events will be captured by applying the MedDRA queries as defined in Table 8. Both overall summary tables and tables by PT will be presented by treatment group for each safety area of interest separately. The following plots will be presented for injection site reactions and abdominal pain:

• Survival probability function plots (one minus the Kaplan-Meier estimator) for the time to the first occurrence of the selected AEs will be presented. Time to the first AE will be calculated from the date of first dose of investigational product.

• Mean cumulative function plots to evaluate recurrent AEs occurring after the date of the first dose of investigational product, showing the mean number of events over time.

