Patients that do not experience the 'event' will be censored at the patient end of trial date. The purpose of these outputs will be to provide a visual presentation of the occurrence over time of these AEs after the first dose of investigation product, rather than any inference or comparison across the treatment groups. AEs with missing (or partially missing) onset date will not be included in these type outputs with a clear statement in a footnote if applicable.

Point prevalence plots with the proportion of patients with events over time will be presented for abdominal pain. The denominator at a specific time point will be the number of patients at risk.

Safety area of interest	Methodology
Gastrointestinal stenosis and intestinal obstruction (including stoma complications)	SMQ 'Gastrointestinal obstruction' (narrow scope) combined with HLT 'Stoma complications' (all terms)
Gallbladder and biliary disease	SMQ 'Biliary tract disorders' (narrow scope) combined with HLT 'Cholecystitis and cholelithiasis' (all terms)
Fluid retention and fluid overload	SMQ 'Haemodynamic oedema, effusions and fluid overload' (narrow scope)
Abdominal pain	HLT 'Gastrointestinal and abdominal pains (excl oral and throat)' (all terms)
Hypersensitivity reactions	SMQ 'Hypersensitivity' (broad scope)
Injection site reactions	Tick mark for 'study treatment injection site reaction' in eCRF (AE form)
Cardiac adverse events	SMQ 'Cardiac arrhythmias' (narrow scope) combined with SMQ 'Cardiac failure' (narrow scope)
Renal adverse events	SMQ 'Acute renal failure' (broad scope)
Hepatic adverse events	SMQ 'Hepatic disorders' (broad scope)
Rare events	CMQ based on EMA Designated Medical Event list, 2020 ¹

Table 8 Methodology for capture of adverse events relevant for other safety areas of interest

¹ https://www.ema.europa.eu/en/documents/other/designated-medical-event-dme-list_en.xlsx **Abbreviations**: CMQ: customized MedDRA query; EMA: European Medicines Agency; HLT: higher level term; MedDRA: Medical Dictionary for Regulatory Activities; SMQ: standardized MedDRA query

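### Adverse events with only a partial onset date are left out of the time-to-first-event and mean cumulative function plots, so these descriptive curves run low or late

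*SAP*

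**What the plan says.** SAP section 7.2 introduces the plots with "The following plots will be presented for injection site reactions and abdominal pain". One is a time-to-first-event curve (one minus Kaplan-Meier, timed from first dose). The other is a mean cumulative function for recurrent events.

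Three statements govern them:

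- Censoring: "Patients that do not experience the 'event' will be censored at the patient end of trial date".
- Purpose: a visual display of occurrence over time, "rather than any inference or comparison across the treatment groups".
- Incomplete dates: "AEs with missing (or partially missing) onset date will not be included in these type outputs", and the same sentence promises a footnote saying so where this applies.

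Two other rules in the same section bear on the point. For a different missing field the plan takes the worst case: "Any missing severity will be imputed as severe prior to selecting the report that will contribute to the summary", with the same logic for relatedness. And treatment-emergent status rests on the date: "Treatment-emergent AEs are defined as AEs with onset date on or after the first day of exposure to investigational product". Neither the SAP nor the protocol gives a rule for imputing an incomplete onset date. Protocol section 11.4.2 lists onset date and time among the minimum information for every adverse event.

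**The concern.** The exclusion treats a date that lacks only the day in the same way as a date that is wholly unknown. The first kind places the event within about a month; the second says nothing about timing. Dropping both has three consequences.

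- A patient whose only event of the type is incompletely dated contributes no event to the Kaplan-Meier curve.
- A patient whose first event is incompletely dated but who has a later, fully dated one gets a first-event time that is too late.
- The mean cumulative function loses each dropped event, though the patient's other dated events remain.

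At stake is the accuracy of the early and final parts of two descriptive curves for reactions expected with this drug. Protocol section 4.3.2 reports that injection site reactions in the Phase 2 trial depended on dose, and lists abdominal pain among the events seen in more than 20% of patients. The missing date rule also leaves treatment-emergent status undetermined for some events.

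**Working it through.** **No plan figure to reproduce.** The documents give no expected frequency for these plots and no count of incomplete dates. What follows shows scale under stated assumptions.

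**1. Final height of the time-to-first-event curve.** Input from the documents: n = 36 per arm (Protocol section 7.1). Assumptions: all patients followed to Day 169, x = 14 with at least one event, and k of these with only an incompletely dated event. Without earlier censoring, one minus Kaplan-Meier at the end is a simple proportion:

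- event kept: x/n
- patient censored at end of trial: (x − k)/n, a loss of k/n
- patient removed from the plot: (x − k)/(n − k)

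| k | kept | censored | removed |
|---|---|---|---|
| 1 | 14/36 = 38.9% | 13/36 = 36.1% | 13/35 = 37.1% |
| 2 | 38.9% | 12/36 = 33.3% | 12/34 = 35.3% |
| 3 | 38.9% | 11/36 = 30.6% | 11/33 = 33.3% |

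The loss under censoring is 1/36 = 2.8 points per patient whatever x is. Removal also lowers the curve, but by less. With x = 8 and k = 1 it reads 7/35 = 20.0% against 22.2%; with x = 20 and k = 1, 19/35 = 54.3% against 55.6%.

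**2. Mean cumulative function.** Under the same follow-up, each dropped event costs 1/36 = 0.028 events per patient.

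**3. Patients with several events.** Assume a true 24-week risk of 40%, onset uniform over 24 weeks, and a share p of events incompletely dated, independently of each other.

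- One event per affected patient: the final value is 40% × (1 − p).
- 1 + Poisson(2) events per affected patient: the final value is 40% × (1 − p·e^(−2(1−p))). The Week 4 value is 40% × (1 − (1 − q)·e^(−2q)), where q = (1 − p)/6 is the chance that an event is both fully dated and in the first 4 of 24 weeks.

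| p | final, one event | final, several | Week 4, several |
|---|---|---|---|
| 0 | 40.0% | 40.0% | 16.1% |
| 5% | 38.0% | 39.7% | 15.5% |
| 10% | 36.0% | 39.3% | 14.8% |
| 20% | 32.0% | 38.4% | 13.4% |

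When events recur, the final height is nearly right and the early part of the curve suffers most. The mean cumulative function is low by the share p itself.

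**4. Treatment-emergent status.** If the recorded month is later than the month of first dose, the definition is met without a day. If it is the month of first dose, or the date is wholly missing, the definition gives no answer and no other rule supplies one.

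**The case against.** The strongest reply is that the rule is pre-specified, will be disclosed on the output, and applies to plots from which the SAP disclaims inference and comparison. Treatment comparison of these event types is by risk difference with 95% confidence interval, and the exclusion is not stated there. Onset date is a required field, adverse events are asked about at each contact (Protocol section 11.4.2), and discrepant data are queried (Protocol section 14.1), so incomplete dates should be few. Putting a wholly missing date on Day 1 could also create a false early cluster. All of this stands. It limits the importance of the point and rules out Day 1 imputation. It does not justify discarding partial dates: a footnote discloses the loss without correcting it, and occurrence over time is what the plots are meant to show.

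Four stronger readings are tempting and are not supported.

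- *The plan orders patients with a known reaction to be censored as event-free.* It censors patients who do not have the event and is silent on this patient. Censoring is only the likely result in code.
- *These are the only displays of when and how often the reactions occur.* Section 7.2 also plans patient counts, percentages, event counts and rates, a table of injection site reaction symptoms, and point prevalence plots for abdominal pain.
- *An incompletely dated event reaches no treatment-emergent output.* Many partial dates meet the definition as they stand, and an exclusion written for one kind of output suggests that the events stay in the others.
- *The treatment comparison is tilted towards the drug.* The plots are not the comparison, and nothing shows that incomplete dates differ by arm, although an arm with more events has more to lose.

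**Conclusion.** The point holds as a minor one. As written, the rule lowers or delays two descriptive plot types for two event categories, whether an affected patient is censored or removed. (A delayed first event can slightly raise the late curve if other patients are censored in between; this is a small exception.) The size is about 2.8 percentage points on the final curve for each patient whose only event is incompletely dated. That assumes 36 per arm, follow-up to the end, and censoring as the implementation. The number of such patients is unknown and probably small, and with none the effect is zero. The simulated-risk figures rest on an assumed 40% risk and assumed shares of incomplete dates, so they show direction and scale only. Efficacy results, alpha and power are not affected.

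**What to change.** Replace the exclusion in SAP section 7.2 with a rule in three parts:

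1. **Partially missing onset date.** Impute the earliest date consistent with the recorded parts, but not before first dose unless those parts or the end date show earlier onset. Use the imputed date for treatment-emergent status and include the event in both plot types.
2. **Wholly missing onset date.** Treat the event as treatment-emergent unless its end date shows otherwise, and leave it out of the timing plots.
3. **Footnote.** Give by arm the number of events imputed, and the number of events and patients left out. State how a patient whose only event is left out enters the Kaplan-Meier curve.

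This matches the cautious rule already used for missing severity and closes the gap in the treatment-emergent definition. It costs a few sentences in the SAP and a few lines of dataset code. The downside is that some events are placed too early, by at most 30 days when only the day is missing. A date with only the year recorded could move further, so such events should be counted separately in the footnote.

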4.1 Background

Patients with short bowel syndrome (SBS) are characterized by reduced intestinal absorptive surface area due to extensive surgical bowel resection or congenital diseases, such as recurrent Crohn's disease or mesenteric vascular disease^{1,2,3,4}, resulting in decreased absorptive capacity of the gut.⁵ This causes a reduced uptake of nutrients, fluids, electrolytes, vitamins, and trace elements, leading to difficulties with maintaining metabolic balances when receiving a conventional diet.⁶ The malabsorption can lead to dehydration, malnutrition, and weight loss if left untreated.⁷

Whereas less severely affected SBS patients are able to compensate for their malabsorption by increasing oral intake (hyperphagia) and adapt metabolically or pharmacologically, more severely affected patients depend upon the safe and well-adjusted provision of parenteral support of nutrients, fluids, electrolytes, vitamins, and trace elements to maintain body function, growth, homeostasis, and health.⁸ For those dependent on parenteral support (PS), it is life-sustaining but at the same time associated with life-threatening complications. Among those are blood stream infections or sepsis,⁹ central vein thrombosis, liver damage¹⁰, and renal impairment.¹¹ In addition, the treatment burden of parenteral support is substantial. Often 10-18 liters of parenteral support per week are required. In addition to 10- to 12-hour over-night parenteral support infusions in such patients, additional hours during daytime may be required to compensate for losses. While liberating patients during daytime, night-time infusions disturb sleep and exacerbate the need for nocturnal urination. Adding to the treatment burden, patients on parenteral support often need frequent follow-up checks at the hospital, and for many there is a need for help from a homecare nurse.

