8.7.3 Algorithm for Parenteral Support Adjustments during Trial Drug Treatment

In general, patients should remain well hydrated during the trial. The urine production should stay above 1 L per day for all patients and the targeted daily urine production should be close to the baseline urine production for the individual patient.

Changes to the content of PS are left to the discretion of the Investigator. Once trial drug treatment is initiated, PS volume can be adjusted at Weeks 1, 2, 4, 8, 12, 16, 20, and 24 if the criteria for adjustment are met and according to the pre-defined algorithm below. Unscheduled visits (preceded by a 48-hour measurement period) may be considered by the Investigator as medically appropriate to adjust PS.

Prerequisite for PS volume reduction:

IF: daily average urine volume of the current visit is at least 10% higher than baseline urine volume.

THEN: New PS volume (weekly) = Current PS volume (weekly) – 7 × absolute increase in daily urine volume from baseline.

Algorithm

New PS volume (weekly) =

Current PS volume (weekly) – 7 x (daily current urine volume – daily baseline urine volume)

Note: The current PS volume is defined as the latest prescribed PS volume, i.e. the PS volume that the patient should be following prior to the visit.

Example:

Patient receives 10 L of PS per week. The urine volume has increased from 1.3 L per day to 1.5 L per day. Hence, the urine volume has increased by more than 10% and PS volume should be reduced. The new weekly PS volume should be 8.6 L (detailed as 10 L – 7 × 0.2 L).

In cases where a patient may not have been fully compliant with the adherence to the prescribed PS volume, the drinking menu, and/or may have missed a urine measurement (e.g., in case the patient has missed to report a urine measurement during the 48 hour measurement period), the Investigator may still perform adjustments to the new PS volume at the Investigators discretion, in order to best match the needs of the patient and in adherence with the algorithm stated above. In that case, the reason for the change must be documented in the eCRF.

The patients should be instructed to contact the clinical site in case urine production falls below normal and if their clinical status changes.

Increasing PS volume:

Increasing PS volume should be considered if laboratory parameters indicate safety concerns. If the average urine production falls below 1 L per day, the Investigator should consider increasing PS volume.

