11.4.1.2 Adverse Events of Special Interest (AESI)

In this trial the following events are to be regarded as AESI, should they occur: neoplasms (malignant and benign), suspicion of liver injury, pancreatitis, and cholecystitis.

If the event is reported as an SAE, the timelines for SAE reporting apply. If the event is reported as non-serious AE, it should be reported in the dedicated eCRF page within 2 working days (if at all possible) of Investigator's first knowledge.

The event-specific information that needs to be captured in addition to the standard AE information is presented below:

Neoplasms:

Information on histopathology (date of examination and results), imaging (if imaging is performed), TNM staging, history of cancer (the patient's and family), treatment received for this event, and an event narrative. Copies of images (if performed) should be stored at each site. A retrospective imaging review may be performed if deemed necessary.

Suspicion of liver injury:

Suspicion of liver injury* is defined as:

- ALT or AST increasing more than 3 times from baseline value, or
- ALT or AST $> 5 \times$ ULN and total bilirubin $> 2 \times$ ULN, or
- ALT or AST $> 5 \times$ ULN and INR > 1.5

* In that case, the tests should be repeated at 48-72 hours for evaluation of the event course/confirmation. Furthermore, additional information needs to be provided by the site,

e.g. physical examination, information on alcohol consumption, concomitant therapy (including herbals).

- Narrative of the event should include:
 - Clinical signs and symptoms and how they developed over time. Aspects like e.g. abdominal pain, nausea, vomiting, jaundice, fever, rash, abdominal tenderness, hepatomegaly, splenomegaly, blood pressure, peripheral edema, jugular venous distension, signs of ascites, recent weight gain should be considered and described.
 - Information on relevant medical history, alcohol consumption, and relevant concomitant therapy (including herbals).
 - Lab tests (at local lab, if needed): as a minimum ALT, AST, Bilirubin (direct and total) and INR. Other tests may be warranted as clinically indicated.
 - Imaging diagnostic (ultrasound/CT scan/MRI/Other imaging modality). Copies of images (if performed) should be stored at each site.
 - Biopsy results (if performed).

Pancreatitis:

- Narrative of the event should include

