The number of bowel movements recorded in the eDiary during the 48-hour period prior to baseline and Week 24, and the change from baseline to Week 24 will be presented descriptively. The number of stoma bag emptyings recorded in the eDiary during the 48-hour period prior to baseline and Week 24 will be summarized in a similar manner, for the subset of patients in the FAS who have a stoma.

Measurements of hydrational status

To evaluate the trends on hydration status the urine volume (mL) and the oral fluid intake (mL) recorded by the patients in the eDiary during 48-hour periods prior to the nominal visits will be presented graphically together with the actual weekly PS volume (L/Week) as follows:

- The individual trajectories of 48-hour urine volume (mL), 48-hour oral fluid intake (mL) and weekly PS volume (L) recorded in the patients in the eDiary will be plotted by actual times (start of 48-hour period or visit). Profiles will be gathered in different panels by SBS anatomical classification and treatment group.
- Mean plots of urine volume (mL by 48-hours), oral fluid intake (mL by 48-hours) and actual weekly PS volume (L/Week). Plots by nominal visit and treatment group
 - y1-axis L/Week (for actual weekly PS volume)
 - y2-axis mL/48-hours (for urine volume and oral fluid intake)

25 August 2022

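### The SAP pools fluid-overload events but not volume-depletion events, and it plots urine volume without counting, by arm, patients below the protocol's 1 L/day level

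*SAP*

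**What the plan says.** **Safety areas.** SAP 7.2 chooses its other safety areas of interest for relevance to the SBS population, for known class effects, or for general interest. Table 8 lists ten. The fluid area uses the narrow query "Haemodynamic oedema, effusions and fluid overload". The nearest area on the other side is renal adverse events, captured by the broad acute-renal-failure query. The adverse events of special interest in Protocol 11.4.1.2 are "neoplasms (malignant and benign), suspicion of liver injury, pancreatitis, and cholecystitis".

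**Dehydration in the protocol.** Protocol 4.1 states: "The malabsorption can lead to dehydration, malnutrition, and weight loss if left untreated". Protocol 8.7.3 says that patients should remain well hydrated and adds: "The urine production should stay above 1 L per day for all patients". Below that level the investigator should consider more parenteral support (PS).

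**Urine in the SAP.** SAP 3.5 (hydrational status) begins: "To evaluate the trends on hydration status the urine volume (mL) and the oral fluid intake (mL) recorded by the patients". What follows is individual trajectory plots and mean plots. SAP section 8 records that these plots replace the repeated-measures model of the fluid composite effect in Protocol 12.3.4, of which urine volume was a component.

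**Comparative estimates.** SAP 7.2 gives Miettinen-Nurminen risk differences for serious events, events leading to treatment discontinuation or trial withdrawal, special-interest events, the Table 8 areas, and events occurring in at least 5% of glepaglutide patients. A discontinuation, withdrawal, special-interest or Table 8 category with fewer than five events is only listed.

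**The concern.** The primary endpoint is a reduction in parenteral fluid, so the natural companion question is whether the reduction came at the cost of hydration. By the SAP's own selection rule, relevance to the SBS population, dehydration is a candidate for Table 8, since the protocol names it as a consequence of the disease. Without a grouping, related terms are tabulated one at a time. A modest excess made up of different terms would not be brought together, whereas an excess of oedema and effusion terms would be.

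The protocol also states a urine level for every patient, and the SAP has no table against it. A plot of arm means is a poor tool for finding a minority of patients with low output. Individual trajectories show them, but only if someone reads the level off each panel. The SAP does count threshold crossings elsewhere: section 7.5 tabulates patients meeting QTcF outlier criteria.

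**Working it through.** The plan gives no figure on this point. The one worked number in Protocol 8.7.3 reproduces, 10 − 7 × (1.5 − 1.3) = 8.6 L/week, but does not bear on it.

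**1. How much PS is expected to be withdrawn.** From Protocol 12.7, in L/week divided by 7:
- twice weekly: 4.5/7 = 0.64 L/day
- once weekly: 4.3/7 = 0.61 L/day
- placebo: 2.3/7 = 0.33 L/day

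All three arms are expected to come down, the active arms by about twice as much as placebo. This is PS withdrawn and not net fluid loss, because better absorption is meant to replace it. Whether it did is what hydration summaries should show.

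**2. When a single preferred term gets a risk difference.** With 36 per arm (Protocol 7.1) and the 5% rule applied to either active arm (SAP 7.2), 1/36 = 2.8% does not qualify and 2/36 = 5.6% does. The gap is therefore limited to non-serious events that do not lead to discontinuation or withdrawal, spread over terms with one patient each per active arm.

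**3. What pooling would show (assumed counts).** Five patients in one active arm, each with a different volume-depletion term: no term reaches 5%, yet the pooled figure is 5/36 = 13.9%. Five events also clear the SAP's listing-only limit. Miettinen-Nurminen 95% intervals:
- 5 vs 0 on placebo: +13.9 points (3.5 to 28.8)
- 5 vs 2 on placebo: +8.3 points (−6.5 to 24.2)

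**4. What a mean urine plot shows (assumed values).** If 5 of 36 patients fall from 1.5 to 0.8 L/day, the arm mean moves by 5/36 × 0.7 = 0.097 L/day. With an assumed between-patient SD of 0.5 L/day, the standard error of an arm mean is 0.5/√36 = 0.083, and that of a difference between arms is 0.5 × √(2/36) = 0.118. The shift would not stand out.

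**5. How many patients could lie below 1 L/day behind an acceptable mean (assumed normal distribution, SD 0.4 to 0.5).** With mean 1.5 L/day: 11% to 16%, about 4 to 6 of 36. With mean 1.75 L/day: 3% to 7%, about 1 to 2 of 36.

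**6. Precision of the proposed count (assumed, patients ever below 1 L/day, 36 per arm).**
- 4 vs 2: +5.6 points (−8.8 to 20.8)
- 7 vs 2: +13.9 points (−1.7 to 30.6)
- 9 vs 4: +13.9 points (−4.3 to 32.0)
- 11 vs 4: +19.4 points (0.6 to 37.9)

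The table would be descriptive and imprecise, like the other Table 8 comparisons.

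**The case against.** A reader might infer that the safety summary can show harm from too much fluid but not from too little. The documents do not support that. The SAP plans:
- all events by system organ class and preferred term, again for serious, severe and related events, and a listing of all treatment-emergent events (7.2);
- risk differences for serious events, for discontinuation and withdrawal events, and for any term in two of 36 patients in an active arm (7.2);
- a renal query (Table 8). Whether it contains dehydration terms cannot be checked from the documents;
- creatinine, creatinine clearance, urea nitrogen, sodium and hematocrit with changes from baseline, post-baseline extremes and shift tables (7.3), and heart rate and blood pressure extremes (7.4);
- weight change in bands (3.4);
- individual urine trajectories beside oral intake and PS volume (3.5), where five patients falling to 0.8 L/day could be seen.

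The fluid-overload area has its own limit, since fewer than five events yield only a listing.

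The 1 L/day level is worded as a management target and not as a definition of harm. Stability at entry allows an average of exactly 1 L/day and a 25% deviation between visits (Protocol 6.2). Taking that 25% as a yardstick, a patient at 1.2 L/day reaches 1.2 × 0.75 = 0.9 L/day through variation the protocol accepts. An ever-below count over eight visits would mix such crossings with genuine shortfalls.

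All of this stands. It narrows the point without removing it: none of these displays pools the depletion terms, and none gives a by-arm count below 1 L/day.

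**Conclusion.** Two omissions are established from the text: Table 8 has no volume-depletion grouping, and no analysis counts patients below 1 L/day by arm. The first affects only non-serious events scattered over terms that each stay under 5% in both active arms. The second leaves the protocol's own hydration level to be judged by eye. Dehydration remains partly visible by several other routes, so this is a worthwhile, inexpensive improvement and not a failure of the safety plan.

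The omissions rest on no assumption. The illustrations of size do: the event counts, the urine means and SDs, and the normal distribution are assumed. Zero events on placebo is a favourable choice, since placebo patients are also expected to reduce PS.

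**What to change.** Before unblinding:

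1. Add a dehydration/volume-depletion row to Table 8, with its MedDRA terms listed in advance and the same summaries and Miettinen-Nurminen risk differences as fluid overload.
2. Add a descriptive table by randomized arm of patients whose mean daily 48-hour urine volume is below 1 L, at each visit and at any post-baseline visit. Name the analysis set (FAS or Safety Analysis Set), use all patients in the arm as denominator, and give the Miettinen-Nurminen risk difference.
3. Because patients with a baseline near 1 L/day can cross the line through ordinary variation, also show the count at two or more visits, or split by baseline urine volume.
4. Keep any display at the first visit after a PS reduction descriptive, with no between-arm interval. PS reduction happens after randomization and is expected to differ by arm, so that contrast is not a randomized comparison.

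The cost is one row and one table from 48-hour volumes already collected before the Week 1 to Week 24 visits. The intervals will be wide at about 36 per arm. No clinical rule changes.
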